3.5 Online data collection

The PIS and the consent form will be shared in advance to participants being contacted via phone. Consent will be audiorecorded and contingent on it being given, interviews will be recorded and transcribed. All data will be automatically stored with King's. Researchers will identify any urgent risks during and immediately after phone-based interviews.

☐ *If the identified risk is urgent*

• The researcher should call 999, or ask someone else to call 999. As a secondary action, the researcher can try to contact the participant's caseworker to seek help.

☐ *If the identified risk is non-urgent*

- The individual should be asked if there is someone they would like to contact for support.
- The researcher may offer to inform the case contact, and seek the participant's consent to do this.

3.6 Reporting disclosures to the police

Generally speaking, the research team will not report disclosures of illegal activities by participants to the police.

Any disclosure of illegal activities will be handled in the first instance in terms of risk of harm to the participant or others (per the guidelines on urgent and non-urgent risks given above). For instance, if the researcher comes into information that leads them to believe there is an urgent safeguarding risk relating to an illegal activity, they may deem it necessary to notify the police immediately via 999. However, if possible, the researcher should first discuss this with the Principal Investigator, Project Manager, or delegate.

In general, the research team will be conscious of the fact that unless the researcher has actually seen an offence being committed or has obtained knowledge of the location of prescribed drugs, illegal weapons or stolen goods, information obtained in the course of research is likely to be unreliable and to be considered 'hearsay'. The team will also be conscious that participation in research should not place people in greater hazard that they would otherwise experience in their daily lives, and this includes reporting of their activities to authorities where this wouldn't otherwise occur.

However, if a participant makes a disclosure relating to any of the following types of offences, this may raise a legal or moral duty to report:

- Child protection offences
- Physical abuse of vulnerable adults

 Money laundering and other crimes covered by prevention of terrorism legislation

If a participant makes a disclosure that the researcher believes falls into one of these categories, they should follow the procedure in Section 3, to respond to and document the disclosure.

The Principal Investigator (or delegate) will then review and consider the information and whether it represents a credible disclosure of an illegal activity in one of the above three categories. They may also discuss it with the responsible delivery partner in order to determine whether it is appropriate to report the disclosure to the police.

Participants are informed in the Participant Information Sheet that if they make a disclosure relating to one of the above three categories, the research team may need to report it to the police.

4 Referral to support services

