Annex G: Safeguarding Protocol

Risk and Safeguarding Protocol Project: Personalised Budgets Randomised Controlled Trial

1 Purpose of this protocol

This protocol covers the risk and safeguarding reporting procedures agreed between Greater Change, its partnering charity organisations and researchers for the project entitled 'Greater Change Personalised Budgets Trial'.

For the purpose of this protocol, the following definitions apply:

- **Data collection:** King's College London in collaboration with IFF Research.
- **Research team:** King's College London
- **Responsible delivery partner:** the organisation that completed the initial screening for any individual participant; expected to be the [charity organisations] which joins the project
- Caseworker **contact:** the personal advisor within the responsible charity organisation who is identified as the key support person for any individual participant

King's, Greater Change and the responsible delivery partners will all have a duty of care to safeguard participants during the research project.

This protocol applies to any interactions by anyone in the research team with research participants, prospective participants during the recruitment process, or participants who have been excluded or who have withdrawn from the project. This includes both surveys and interviews, and also interactions via email or phone that may occur from time to time.

2 Definition of Risks

Research team members should use their own professional judgement regarding any situation or issue in which the risk of harm to a participant or others may be reported or inferred. In this section, we provide examples of different types of risks that may arise.

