2.1 Urgent risks

Urgent risks are any risks where the researcher has reason to believe the participant or someone else is in immediate danger. Researchers should consider any of the following to suggest an urgent risk, especially in combination:

- Disclosure of a clear and imminent suicide plan, or disclosure that they have already acted in a way that puts their life in immediate danger
- Disclosure of a clear and imminent plan to harm someone else (or a plan to act in a way that will harm them and others e.g. stepping out in front of a train)
- Severe distress (e.g. crying, aggression, agitation, withdrawal), unstable mood observable by the researcher, or signs of self-harm evident
- Disclosure of actions suggesting an immediate risk of drug overdose (accidental or intentional)
- *In combination with others:* Disclosure of access to a weapon or other means of harm (e.g. medicine, cutting tools)
- *In combination with others:* Disclosure of suicidal thoughts or feelings of hopelessness/helplessness
- *In combination with others:* Disclosure that the participant is alone and/or feels they are experiencing a breakdown in their social circumstances
- *In combination with others:* Disclosure of a history of self-harm, harm of others, or attempted suicide
- Any information that causes the researcher concern that the participant may be in immediate danger
- Any information that causes concern regarding the safety of others

All members of the research team must attend training on identifying and responding to urgent risks, including mental health risks, before they are deployed on the project. All King's researchers must also be up-to-date with King's College London's safeguarding training before being deployed on the project.

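### Annex G 3.6 leaves the order of the 999 call and the discussion with the Principal Investigator ambiguous when someone is in immediate danger

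*Protocol*

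**What the plan says.** All references are to the Protocol, Annex G (Safeguarding Protocol).

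- **Section 2.1** sets the threshold: "Urgent risks are any risks where the researcher has reason to believe the participant or someone else is in immediate danger". Its list of examples includes a clear and imminent plan to harm another person.
- **Sections 3.1 and 3.5** give the action for an urgent risk. The researcher should call 999 or ask someone else to. Section 3.1 adds that the researcher should try to keep the participant on the line and use a separate phone for the call. Section 3.5 ranks contacting the caseworker as secondary. Neither section puts a discussion before the call.
- **Section 3.6** starts from a general position of not reporting illegal activity to the police. It then states: "Any disclosure of illegal activities will be handled in the first instance in terms of risk of harm to the participant or others", and adds in brackets "per the guidelines on urgent and non-urgent risks given above". As an instance of this, it takes the case where the researcher believes that "there is an urgent safeguarding risk relating to an illegal activity" and says "they may deem it necessary to notify the police immediately via 999". The next sentence is: "However, if possible, the researcher should first discuss this with the Principal Investigator, Project Manager, or delegate".
- **Later in 3.6**, three listed offence types have their own route: the researcher follows section 3, and "The Principal Investigator (or delegate) will then review and consider the information".

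**The concern.** The urgent example in 3.6 is offered as an illustration of the guidelines in 3.1 and 3.5, but it states them more weakly. A direction becomes a permission, and a consultation is placed ahead of the call. By the annex's own definition an urgent risk means that someone is believed to be in immediate danger, so the request to discuss first is attached to the cases where time matters most.

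A researcher who hears of an imminent plan to harm a third party could reasonably consult both 3.1 and 3.6 and find two orders of action. Under 3.1 that researcher may be holding the participant on one phone and calling on another, so a prior discussion would take place during the emergency. What is at stake is a possible delay to an emergency call, and with it the safety of participants and third parties. No estimate or test in the trial depends on it.

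**Working it through.** No arithmetic is needed beyond simple counts. The check sets the sections side by side.

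**1. Do 3.1, 3.5 and 3.6 cover the same cases?** Sections 3.1 and 3.5 apply when the identified risk is urgent. The example in 3.6 is expressly an urgent safeguarding risk, and urgency is defined once, in 2.1, as immediate danger. The example in 3.6 is therefore a subset of the cases under 3.1 and 3.5, namely those that also involve illegal activity.

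**2. Do they prescribe the same action?**

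| Section | Strength of the 999 instruction | Step placed before the call |
|---|---|---|
| 3.1 | should | none |
| 3.5 | should | none (caseworker contact is secondary) |
| 3.6, urgent example | may, if judged necessary | discussion with the Principal Investigator, Project Manager or delegate, if possible |

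Three sections give an instruction about calling 999. Two of the three agree; one differs in both strength and order.

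**3. What decides whether the discussion comes first?** The only qualifier in 3.6 is whether the discussion is possible. If a delegate answers the phone, a discussion is possible, and the literal instruction is to have it before the call. Whether the delay is safe is a different test, and 3.6 does not state it.

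**4. How far do the rules overlap?** Section 2.1 lists 10 examples of urgent risk. Four count only in combination with others, which leaves 10 − 4 = 6 that stand alone. Of these, one clearly falls under both rules: the imminent plan to harm someone else. The two general examples (any information causing concern about immediate danger to the participant, or about the safety of others) may also do so, depending on what is disclosed. These counts show overlap in wording. They do not measure how often such a disclosure will occur or what harm would follow, and the protocol gives no expected number.

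**5. Do sections 3.2 and 3.3 add a conflict?** No. Section 3.2 has the concern reported to the Principal Investigator once the interaction has ended, and 3.3 covers the following days. Neither requires or forbids earlier contact, so they are not counted.

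**The case against.** The strongest reply is that the annex already contains the right rule. The cross-reference in 3.6 brings in the urgent-risk guidelines, including the direction to call 999. **This stands in part:** 3.1 and 3.5 remain nominally in force. But the sentences that follow present themselves as an application of that rule and give it in weaker form, and a reader under pressure may follow the specific example.

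A second reply is that 3.6 answers a different question, namely whether to involve the police over an offence, with its issues of confidentiality and hearsay. On that reading the softer verb does not dilute the emergency instruction. The reading is available. However, 3.6 names the same 999 route for the same category of urgent risk, so the text does not keep the two decisions apart.

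A third reply is that the discussion is asked for only where possible, that any of three contacts will do, and that a colleague who is contacted could be the one to call 999. Section 2 also relies on judgement ("Research team members should use their own professional judgement regarding any situation or issue"), and urgent-risk training is compulsory before deployment. **These points stand and lower the practical risk.** They do not correct the written order.

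A reader might infer that 3.6 prohibits an immediate call, or that it makes no allowance at all for immediate danger. The document supports neither. The example itself allows the police to be notified at once, and the qualifier on the discussion works as a partial exception, since it can be read as meaning if circumstances allow.

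**Conclusion.** The point holds as a low-severity ambiguity in safety wording. For a disclosure that is both urgent under 2.1 and about illegal activity, 3.1 and 3.5 direct a 999 call, while 3.6 permits one and asks for a discussion first where that is possible. The order of action is therefore unclear in cases of immediate danger.

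The extent is one of three 999 instructions, with one of ten urgent examples clearly affected and two more possibly. The conclusion assumes that a researcher could read the example in 3.6 literally and on its own. Read together with the cross-reference, the qualifier, the training and the reliance on judgement, the text leaves room for an immediate call. Nothing in the protocol shows that a delay is likely, and the trial's design, outcomes and analysis are unaffected.

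**What to change.** Amend Annex G 3.6 to say that where a risk meets the definition in 2.1, sections 3.1 and 3.5 govern: the researcher calls 999, or asks someone else to, without waiting for discussion, and informs the Principal Investigator, Project Manager or delegate in parallel or immediately afterwards. Limit the discuss-first sentence to disclosures that do not involve immediate danger. Leave the Principal Investigator's review of the three listed offence types as it is.

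The cost is one or two sentences in the annex and a line in the urgent-risk training that is already required. Data collection and analysis do not change.

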4.1 For research team

Upholding the safety of all members of the research team, along with participants, is a priority. The following steps will be taken to ensure that project staff are able to access support, should the need for this arise during the course of the research.

- Each researcher will be matched with a 'buddy' (e.g. a senior researcher with safeguarding expertise) to check-in with regularly.
- Training in issues including vicarious trauma will be provided to ensure researchers feel appropriately equipped to manage difficulties arising from potential safeguarding concerns.
- Regular team discussions and debriefs to share experiences, lessons and best practices will occur to facilitate knowledge sharing within the team.
- Researchers will be reminded of the Employee Assistance Helpline by line managers during regular meetings.

